6.3.3 Power for Comparison

For groupwise difference in immunogenicity, a simple comparison on the positive response rate will be used. Table 4 gives the power of Fisher exact test to compare any two schedules over a range of possible response rates and indicates that this study is not powered for group comparison.

Table 4: Power (%) to Detect Difference in Response Rates between Two groups by Fisher’s Exact Test, Each Group of Size n=5

		Arm 1 Rate (n=5)			
		0.2	0.3	0.4	0.5
Arm 2 Rate (n=5)	0.1	1	1	5	12
	0.2	1	1	3	7
	0.5	7	4	2	2
	0.6	14	8	4	2

6.4 Statistical Analysis

Since randomization is concurrent with receiving the first study vaccination, the expectation is that all randomized participants will receive at least one vaccination and therefore will provide some safety data. All statistical analyses will be performed using Statistical Analysis System (SAS) or statistical software R. No formal multiple comparison adjustments will be employed for safety endpoints or immunogenicity endpoints.

6.4.1 Analysis Variables

The analysis variables consist of baseline variables, safety variables, and immunogenicity variables for primary and secondary objective analyses.

6.4.2 Baseline Comparability

Baseline characteristics including demographics and laboratory measurements will be summarized using descriptive statistics.

6.4.3 Safety Analysis

Reactogenicities

The number and percentage of participants experiencing each type of reactogenicity sign or symptom will be tabulated by severity. For a given sign or symptom, each participant's reactogenicity will be counted once under the maximum severity for all assessments.

Adverse Experiences

Adverse experiences are coded into Medical Dictionary for Regulatory Activities (MedDRA) preferred terms. The number and percentages of participants experiencing each specific adverse event will be tabulated by severity and relationship to treatment. For the calculations in these tables, each participant's adverse experience will be counted once under the maximum severity or strongest recorded causal relationship to treatment.

A complete listing of adverse experiences for each participant will provide details including severity, relationship to treatment, onset, duration and outcome.

Local laboratory values

Boxplots of local laboratory values will be generated for baseline values and for values measured during the course of the study. Each boxplot will show the 1st quartile, the median, and the 3rd quartile. Outliers, or values outside the boxplot, will also be plotted. If appropriate, horizontal lines representing boundaries for abnormal values will be plotted.

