5 SAFETY AND ADVERSE EVENTS

5.1 Adverse Events

An adverse event (AE) is any untoward or unfavorable medical occurrence in a human subject, including any abnormal sign (e.g., abnormal physical exam or laboratory finding), symptom, or disease temporally associated with the use of study treatment, whether or not considered related to the study product.

Each AE will be graded according to the Table for Grading Severity of Adverse Events (see [Appendix IV](#)). The following guidelines will be used to determine when or not an AE should be recorded in the study database:

- From the time that subject signs the ICF, only AE that meet the definition of a SAE as described in Section 5.2 that occur within 24 hours of a screening visit will be reported.
- Solicited AEs (i.e, reactogenicity parameters) will be recorded in the study database per diary card entries for 7 days after each product administration and is not recorded with attribution assessments. Clinicians will follow and collect resolution information for any reactogenicity symptoms that are not resolved within 7 days.
- Unsolicited AEs and attribution assessments will be recorded in the study database from receipt of the first product administration through the visit scheduled for 4 weeks after each product administration. At other time periods between product administrations and when greater than 4 weeks after the last study product administration, only SAEs (as detailed in [Section 5.2](#)) and new chronic medical conditions that require ongoing medical management are recorded through the last study visit.

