6.2 Endpoints

6.2.1 Primary Endpoints: Safety

Assessment of product safety will include clinical observation and monitoring of hematological and chemical parameters. Reactogenicity will be closely monitored for 7 days after each product administration and safety evaluated by clinical visits through the study duration of 36 weeks.

The following parameters will be assessed for all study groups:

- Local reactogenicity signs and symptoms for 7 days after each injection
- Systemic reactogenicity signs and symptoms for 7 days after each injection
- Laboratory measures of safety
- AEs
- SAEs
- New chronic medical conditions

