8.5 Risks and Benefits

8.5.1 Risks of the WEVEE Vaccine

There is no prior human experience with administration of VRC-WEVVLP073-00-VP in healthy adults. First human clinical trials of a similar VLP vaccine, VRC 311 - CHIKV VLP, determined that doses in the range of 10-40 mcg were safe for further evaluation in healthy adults. The solicited local and systemic signs and symptoms following administration of the CHIKV VLP were generally none to mild. In VRC 311, seven laboratory test AEs (occurring in four participants) were assessed as related to study vaccine based on temporal relationship to vaccination. The AEs included four mild transient alanine aminotransferase increases and two mild and one moderate transient neutropenia. All resolved without clinical sequelae.

This alphavirus CHIKV VLP vaccine was advanced to Phase 2 clinical evaluation in November 2015 in protocol VRC 704. As of November 13, 2017, 400 subjects have received a total of 780 injections of VRC-CHKVLP059-00-VP or placebo. There have been no serious adverse events (SAEs) assessed as related to the study product reported in the study and no AEs that required expedited reporting to the FDA. Abnormalities in blood laboratory parameters observed in the study were asymptomatic, predominantly mild or moderate in severity. The local and systemic reactogenicity signs and symptoms following administration of the CHIKV VLP were generally mild to moderate. All abnormalities in blood laboratory parameters, solicited local and systemic reactogenicity signs and symptoms were resolved without clinical sequelae.

Potential side effects resulting from IM injection include stinging, arm discomfort, redness of the skin or mild bruising at product administration sites.

Subjects may exhibit general signs and symptoms associated with administration of a vaccine, including fever, chills, rash, aches and pains, nausea, headache, dizziness and fatigue. These side effects will be monitored, but are generally short term, mild to moderate severity and usually do not require treatment.

There may be other unknown side effects.

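### Apart from abnormalities recorded as AEs, post-baseline laboratory safety is planned only as boxplots, and at 3 of 7 post-dose visits non-serious, non-chronic graded abnormalities reach no planned table or listing

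*Combined protocol and SAP*

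**What the plan says.** Section 6.2.1 lists "Laboratory measures of safety" among the primary safety parameters, on a separate line from AEs and SAEs.

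Section 6.4.3 treats the components differently. Reactogenicity and AEs are tabulated by severity, with each participant counted once at the maximum, and AEs are also listed by participant. For laboratory values the plan is: "Boxplots of local laboratory values will be generated for baseline values and for values measured during the course of the study". It adds "Outliers, or values outside the boxplot, will also be plotted" and "If appropriate, horizontal lines representing boundaries for abnormal values will be plotted". It names no post-baseline table by grade, no shift from baseline and no laboratory listing. Section 6.4.2 adds descriptive statistics, for baseline only.

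Section 5.1 counts an abnormal laboratory finding as a possible AE and grades AEs by Appendix IV. It records unsolicited AEs and their attribution "through the visit scheduled for 4 weeks after each product administration". At other times only SAEs and new chronic conditions needing ongoing management are recorded.

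Appendix III schedules CBC and ALT at Visits 03 to 09, and creatinine at screening, Visit 02 and Visit 05. The schedules attached to Letters of Amendment 1 and 3 leave these draws unchanged.

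**The concern.** The AE tables and listing are the only planned route by which a post-baseline laboratory abnormality is counted by grade and tied to a participant. That route closes after Visit 04 and reopens with dose 2, then closes again after Visit 07, while safety blood is still being drawn. For those later draws the only planned output is a plot. No participant identifier or grade is required on it, and limit lines are optional.

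The related laboratory events in the first trial of the sister chikungunya vaccine, described in section 8.5.1, were "four mild transient alanine aminotransferase increases and two mild and one moderate transient neutropenia". Findings of that kind are usually neither SAEs nor new chronic conditions. A similar finding at Visit 05, the last look before dose 2, could be missing from every count in the final report.

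Entry limits also overlap Grade 1 for ALT, lymphocytes and platelets. Some participants may therefore start with a gradeable value, and a boxplot cannot separate a new grade from an old one.

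**Working it through.** **The plan's own figure.** Section 6.3.1 gives 0.522 as the exact two-sided 95% upper bound for 0 of 5. The formula is 1 − 0.025^(1/n). At n = 5 this is 1 − 0.025^(1/5) = 0.522, which reproduces Table 3.

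**Visits against the AE window.** Inputs are the visit days in Appendix III and the window in section 5.1. Section 4.2.6 requires blood to be drawn before product is given, so Visit 05 blood precedes dose 2.

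| Visit | Day | Days since last dose | Unsolicited AEs recorded? |
|---|---|---|---|
| 03 | 14 | 14 | Yes |
| 04 | 28 | 28 | Yes |
| 05 | 56 | 56 | No |
| 06 | 70 | 14 | Yes |
| 07 | 84 | 28 | Yes |
| 08 | 168 | 112 | No |
| 09 | 252 | 196 | No |

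Three of seven CBC/ALT visits are outside. For creatinine, the single post-dose draw (Visit 05) is outside: 1 of 1.

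**Visit windows do not change this.** The latest in-window Visit 04 is Day 28 + 7 = 35, and the earliest Visit 05 is Day 56 − 7 = 49. The latest Visit 07 is 28 + 7 = 35 days after dose 2, and the earliest Visit 08 is 112 − 14 = 98 days after it.

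**Size.**
- At 30 participants: 7 × 30 = 210 post-dose CBC/ALT panels, of which 3 × 30 = 90 are outside; 90/210 = 43%.
- At the maximum of 40: 7 × 40 = 280 panels, of which 3 × 40 = 120 are outside; the share is the same.

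**Overlap of entry limits (section 4.1.1) with Grade 1 (Appendix IV).**
- ALT: entry up to 1.25 × ULN, Grade 1 from 1.1 × ULN; overlap 1.1 to 1.25 × ULN.
- Lymphocytes: entry from 800, Grade 1 750 to 1,000; overlap 800 to 1,000 cells/mm³.
- Platelets: entry from 125,000, Grade 1 125,000 to 140,000; overlap 125,000 to 140,000/mm³.

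Appendix IV does not grade values inside the institutional normal range. The documents do not give those ranges, so the effective overlap may be narrower.

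**What a per-participant count would allow.** With every visit graded, exact bounds apply directly. Zero events would give upper 95% bounds of 0.522 (0/5, one group), 0.308 (0/10, one dose level), 0.218 (0/15, one adjuvant arm) and 0.116 (0/30, all participants).

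**The case against.** The other side has several good points.

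- A reader might infer that laboratory safety as a whole is summarised only by boxplots. The documents do not support that: in-window abnormalities recorded as AEs are tabulated by severity and relationship and listed, and baseline values get descriptive statistics.
- A reader might infer that late abnormalities vanish. They do not: SAEs and new chronic conditions are recorded to the last visit, and the boxplots cover the whole study with outliers shown. Day 0 remains the baseline (section 4.2.4), so an abnormality first seen at Visit 05 and still present at Visit 06 or 07 could be recorded in the dose-2 window.
- A reader might take 43% as the share of abnormalities missed. That would need abnormalities to be equally likely at every visit. Section 8.5.1 says the sister-vaccine findings were judged related because of their timing after vaccination, and the covered visits are those at 14 and 28 days. The missed share of vaccine-related transient changes is probably lower; the documents give no figure.
- A reader might picture boxplots of five values. Section 6.4.3 does not say how the plots are grouped, so a box could hold five values or all 30.
- Section 8.8.1 provides daily site review, and safety-team review weekly and then monthly. The gap is in planned reporting, not oversight.
- The AE window is a deliberate choice, and attribution is recorded only inside it. Late grades would carry no causality assessment and must be labelled accordingly.

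These points narrow the finding but do not close it. None supplies a count or listing for a non-serious, non-chronic graded result that is seen only outside the window.

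**Conclusion.** The point holds in limited form. For a separately listed primary endpoint, graded CBC and ALT abnormalities first seen at Visits 05, 08 and 09, and any graded creatinine at Visit 05, have no planned table or listing unless they are SAEs or new chronic conditions. The affected share is 3 of 7 post-dose CBC/ALT visits, or 90 of 210 panels at 30 participants, and the only post-dose creatinine. No estimate of lost abnormalities can be drawn from this.

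The conclusion rests on reading Visit 05 blood as drawn before dose 2, as section 4.2.6 requires, and on section 6.4.3 being the full list of laboratory outputs. It does not imply that safety monitoring is deficient or that the AE window is wrong. The change is worth making because it can alter the abnormality counts reported for a primary endpoint and uses data the trial already collects.

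**What to change.** In section 6.4.3, add the following to the laboratory paragraph:

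1. Grade every scheduled CBC, ALT and creatinine result by Appendix IV, whether or not it falls in the AE window. Keep the rule that values within the institutional normal range are not graded.
2. Tabulate Day 0 grade against worst post-baseline grade, counting each participant once per parameter, by group and pooled by adjuvant. Where a Day 0 result is missing, use the screening value, as section 4.2.4 allows.
3. List all graded values by participant and visit, marking those outside the AE window as having no causality assessment.

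The boxplots can stay. Showing individual participant values instead of boxes is a matter of presentation.

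Visits, blood volumes, AE collection windows and clinical conduct do not change. The cost is modest programming on data and a grading scale already in place.

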6.4.4 Immunogenicity Analysis

The statistical analysis for immunogenicity will employ the intent-to-treat principle, i.e., all data from randomized participants will be used. In the final analysis of immunogenicity, if there are cases of a subject receiving a schedule different from the assignment, then an as-treated analysis will be performed.

If assay data are qualitative (i.e., positive or negative) then analyses will be performed by tabulating the frequency of positive response for each assay at each time point that an assessment is performed. Binomial response rates will be presented with their corresponding exact 95% confidence interval estimates. Fisher's exact tests will be used to compare the two vaccine groups to each other. Missing responses will be assumed to be missing at random, i.e., conditional on the observed data the missingness is independent of the unobserved responses. Graphical descriptions of the longitudinal immune responses will also be given.

Some immunologic assays have underlying continuous or count-type readout that is often dichotomized into responder/nonresponder categories. For these assays, graphical and tabular summaries of the underlying distributions will be made. These summaries may be performed on transformed data (e.g., log transformation) to better satisfy assumptions of symmetry and homoscedasticity.

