1.2 Rationale for the Development of the WEVEE Vaccine

Alphaviruses have been responsible for multiple epidemics in various parts of the world. There is no effective antiviral treatment or licensed vaccine for any of these encephalitic arboviruses

and treatment is with supportive measures only. Additionally, prevention of viral infection is of particular interest because of the potential use of these viruses as biological weapons.

VLPs are multiprotein structures that mimic the organization and conformation of authentic native viruses without the viral genome. Due to the absence of the viral genome, the VLPs cannot replicate. VLPs contain viral surface proteins that present repetitive linear and conformational epitopes capable of eliciting strong T and B cell immune responses and therefore, are useful as vaccines.

VRC previously developed VRC-CHKVLP059-00-VP, a Chikungunya virus (CHIKV) VLP vaccine. This vaccine demonstrated induction of neutralizing antibodies and protection against CHIKV infection by percutaneous exposure in a rhesus macaque model [8]. Under IND 14907, a Phase 1 clinical trial demonstrated that the vaccine was safe and highly immunogenic in healthy adults [9] and a Phase 2 clinical trial in CHIKV-endemic regions is pending final analysis.

VRC-WEVVLP073-00-VP (or WEVEE) is a trivalent WEE, EEE, and VEE VLP vaccine produced by the same methods as the CHIKV VLP vaccine and is intended to elicit broad spectrum protection against targeted alphaviruses.

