1.3 Rationale for the Use of Aluminum–Based Adjuvant

Adjuvants improve the immune response to many vaccines [10, 11]. The most common aluminum-based adjuvants includes aluminum hydroxide, aluminum phosphate, alum (potassium aluminum sulfate), or mixed aluminum salts [12, 13]. Several phenomena contribute to the effect of aluminum hydroxide based adjuvants: a ‘repository effect’ which occurs when the antigens aggregate on the adjuvant particle and are deposited to the immune cell for long duration to induce immune responses, a pro-phagocytic effect, and possibly the activation of the pro-inflammatory nucleotide like receptor protein 3 (NLRP3) dependent pathways [13]. Aluminum-based adjuvants often improve humoral and innate responses and may lead to increased antibody titers, rapid induction of responses, reduction in size or frequency of doses, increased breadth of responses to overcome pathogen diversity, induction of long-lasting immune memory responses, and induction of response to overcome poor immune systems in elderly and young children [14-17]. Aluminum is generally well tolerated, and adjuvants have a demonstrated safety profile over more than six decades of use [14, 15].

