4 STUDY DESIGN AND CLINICAL PROCEDURES

This is a Phase I, randomized, open-label, dose-escalation study to examine the dose, safety, tolerability, and immune response to the WEVEE vaccine alone or with alum adjuvant at three doses (6 mcg, 30 mcg, and 60 mcg) in healthy adults. Eligible subjects will be randomized to WEVEE alone or WEVEE plus alum administration in each dose group. The product will be administered IM in the deltoid muscle via needle and syringe at Day 0 and Week 8 in each dose group. The hypotheses are that this vaccine will be safe and elicit specific immune responses to WEE, EEE and VEE viruses.

Group assignments and study schema are shown below in [Table 1](#):

Table 1: VRC 313 Vaccination Schema

VRC 313 Vaccination Schema				
Group	Subjects	Dose	Day 0	Week 8
1	5	6 mcg	WEVVEE	WEVVEE
2	5		WEVVEE + alum	WEVVEE + alum
3	5	30 mcg	WEVVEE	WEVVEE
4	5		WEVVEE + alum	WEVVEE + alum
5	5	60 mcg	WEVVEE	WEVVEE
6	5		WEVVEE + alum	WEVVEE + alum
Total*	30	*Up to 10 subjects over target accrual are permitted to be allocated to any group for additional safety or immunogenicity evaluations.		

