6.5 Randomization of Intervention Assignments

Randomizations will be done online using an electronic randomization system. The randomization code will be prepared by the Protocol Statistician and included in the randomization module for the trial. The randomization code will link to the intervention assignment. The electronic data system will assign each subject a randomization code after eligibility has been confirmed in the system.

At the beginning of the study, subjects will be randomized 1:1 to Groups 1 and 2. If the criteria for the first dose escalation are met and procedures for the interim safety review are completed, subjects can be randomized 1:1 to Groups 3 and 4. For practical purposes, accrual and randomization to Groups 1 and 2 should be completed as per study plan before accrual to Groups 3 and 4 begins.

If the criteria for the second dose escalation are met and procedures for the interim safety review are completed, subjects can be randomized 1:1 to Groups 5 and 6. For practical purposes, accrual and randomization to Groups 3 and 4 will be completed as per study plan before accrual to Groups 5 and 6 begins.

The subject and study clinicians will be informed on the subject's group assignment upon completing randomization in the electronic data collection system.

To decrease the potential for subject dropouts during the period between randomization and product administration will occur on Day 0 when eligibility is confirmed. If subjects accrued to a study group do not complete the number of vaccinations and follow-up duration specified, then additional subjects may be accrued in that group.

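### The randomised contrast, alum against no alum within dose, has no planned titre estimate; groups are compared only by Fisher's test on response rates, between two groups not identified.

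*Combined protocol and SAP*

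**What the plan says.** - **Comparison of groups.** For qualitative results, section 6.4.4 gives response rates with exact 95% intervals and says Fisher's "exact tests will be used to compare the two vaccine groups to each other". Section 6.3.3 says "Table 4 gives the power of Fisher exact test to compare any two schedules over a range of possible response rates", with 5 per group, and that it "indicates that this study is not powered for group comparison".
- **Titres.** For assays with a continuous readout, section 6.4.4 says: "For these assays, graphical and tabular summaries of the underlying distributions will be made". A log transformation is allowed. No GMT ratio, difference, between-group interval or model is named.
- **Randomisation.** Section 4: "Eligible subjects will be randomized to WEVEE alone or WEVEE plus alum administration in each dose group". Section 6.5 adds that "accrual and randomization to Groups 1 and 2 should be completed as per study plan before accrual to Groups 3 and 4 begins", with a matching rule before Groups 5 and 6. Dose is therefore not randomised.
- **Objectives.** Section 3.2 evaluates neutralising response without adjuvant and, separately, with adjuvant, 4 weeks after the last administration. No comparative objective is stated.
- **Rationale for alum.** Section 1.3: "Aluminum-based adjuvants often improve humoral and innate responses and may lead to increased antibody titers".

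**The concern.** The plan commits to a group comparison but leaves two things open.

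First, the two groups to be compared are not named. Six groups give 6 × 5 / 2 = 15 possible pairs. Some of these differ in dose as well as alum, and so compare subjects enrolled at different times.

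Second, the comparison uses only the responder/non-responder split, while the stated reason for alum includes higher titres. The contrast that randomisation protects is repeated at three doses, 15 v 15 in all, yet no planned titre estimate uses it. What is at stake is how much the trial can say about alum from data it already collects. The primary safety aim is not affected.

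**Working it through.** **1. The plan's own figure.** Enumerating both binomials (n = 5 each) with a two-sided Fisher test at 0.05 (assumed, as the plan states no alpha) reproduces all 16 cells of Table 4 to within one percentage point. Examples: 0.2 v 0.6 gives 14.2 (stated 14), 0.1 v 0.5 gives 12.1 (stated 12), 0.2 v 0.5 gives 7.5 (stated 7). Table 4 is sound.

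**2. Fisher's test at 5 v 5 and at 15 v 15.** At 5 v 5 the test rejects only at 0 v 4, 0 v 5 or 1 v 5 responders. If all alum subjects respond, power is the chance of 0 or 1 responders among five without alum, (1−p)^5 + 5p(1−p)^4:

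- p = 0.9: 0.00001 + 0.00045 = 0.05%
- p = 0.8: 0.00032 + 0.0064 = 0.7%
- p = 0.6: 0.01024 + 0.0768 = 8.7%

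If the sentence means alum against none over all doses, the test is 15 v 15. The last column is an exact test stratified by dose. Rates are assumed, and equal at each dose.

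| Rate, none v alum | Fisher 5 v 5 | Fisher 15 v 15 | Stratified exact |
|---|---|---|---|
| 90 v 100% | 0.05% | 1.3% | 1.3% |
| 80 v 100% | 0.7% | 16% | 17% |
| 60 v 100% | 8.7% | 78% | 78% |
| 20 v 60% | 14% | 45% | 47% |

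Which groups are compared matters a great deal. Stratifying the 15 v 15 test adds essentially nothing.

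**3. Titre.** Inputs: 5 per group (section 6.3); log10 SD of 0.4 to 0.6 (assumed); uncensored, normal log titres with a common SD. The 95% CI for the alum GMT ratio is the estimate ×/÷ 10^(t × SE).

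- Dose as a factor: df = 30 − 4 = 26, t = 2.056, SE = SD × √(2/15) = 0.146 to 0.219. Factor 10^0.300 to 10^0.450 = **2.0 to 2.8**.
- One 5 v 5 pair: df = 8, t = 2.306, SE = SD × √(2/5) = 0.253 to 0.379. Factor 10^0.583 to 10^0.875 = **3.8 to 7.5**.
- Per-dose ratios from one model with interaction: df = 24, t = 2.064, same SE as one pair. Factor **3.3 to 6.1**.

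The smallest common ratio detectable with 80% power (noncentral t) is 1.063 SD over dose, or 2.7 to 4.3-fold. In one pair it is 2.024 SD, or 6.5 to 16-fold. A wider assumed SD of 0.3 to 0.7 gives an over-dose factor of 1.7 to 3.4.

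**4. What averaging over dose can hide.** If alum raised titre 9-fold at one dose and not at all at the other two, the combined ratio would be (9 × 1 × 1)^(1/3) = 2.1. A dose-by-alum interaction test (2 and 24 df) would detect that with 74% power at SD 0.4 and 39% at SD 0.6.

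**5. Is response likely to be complete?** The documents point both ways. Section 1.2 describes this vaccine as "produced by the same methods as the CHIKV VLP vaccine", and section 1.4.1 reports neutralising antibody to that vaccine in every subject by 4 weeks after dose 2. Section 1.4.2 reports, for earlier vaccines against these same viruses, response rates of 42% (WEEV), 66% (EEEV), and 66.7% or 80.6% (VEEV, by order of vaccination). Those were not VLP products. The chikungunya doses were 10 to 40 mcg (section 8.5.1), whereas 6 mcg of a 1:1:1 mixture is 6 / 3 = 2 mcg per virus.

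**The case against.** The strongest reply is that nothing is wrong with the plan as a descriptive one. No objective compares alum with none, section 6.3.3 openly says the study is not powered to compare groups, and summaries by group serve the stated objectives. That stands, and it caps the importance of the point. It does not remove it: section 6.3.3 still commits to a comparison, its remark on power rests on 5 v 5 response rates alone, and low power is a reason to plan an interval rather than a test. A ratio could be worked out later from the summaries, but it would then be post hoc.

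Three stronger readings are tempting and are not supported.

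- *The planned test is 5 v 5 and therefore almost useless.* Table 4 supports 5 v 5, but section 6.4.4 gives no size, and its words could mean the two formulations, 15 v 15. The defect is that the comparison is undefined.
- *Response will be near complete, so response rates say nothing.* That is borrowed from another vaccine, and the rates in section 1.4.2 point the other way.
- *The 10 permitted extra subjects would sharpen the randomised contrast.* The note to Table 1 allows them in any group, so they need not be randomised 1:1 between formulations. No precision is claimed for them here.

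It is also fair that the combined ratio averages over a tenfold dose range and may describe no single dose, and that the per-dose ratios remain imprecise.

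**Conclusion.** The point holds as a gap in estimation, not as an error in a stated figure. The only planned between-group comparison of immunogenicity is Fisher's test between two unidentified groups, and the one randomised contrast has no planned titre estimate. A dose-adjusted GMT ratio would narrow the 95% CI factor from 3.8 to 7.5 (one pair) to 2.0 to 2.8.

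Those figures rest on 5 evaluable subjects per group, an assumed SD, titres above the assay limit and an alum effect of similar size at each dose. Precision is worse if many titres lie below the limit. The titre estimate adds most if response is near complete, because response rates then carry little information. With three viruses and no multiplicity adjustment (section 6.4), the ratios should be read as estimation, not as tests. The gain is modest.

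**What to change.** In section 6.4.4:

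1. For each virus at 4 weeks after the second vaccination, estimate the alum v no-alum GMT ratio with 95% CI from log10 neutralising titre, with dose as a factor. Name a censored-data method, for example a Tobit model, for use if titres fall below the assay limit.
2. Show the ratio at each dose beside it, labelled descriptive.
3. State that any Fisher comparison is alum against none, within dose or stratified by dose. The stratified form is for clarity, not power.
4. State that the ratios are for estimation, across three viruses and without multiplicity adjustment.

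The cost is a few sentences and minor programming. No further subjects, visits or samples are needed. The price in interpretation is the averaging over dose, which is why item 2 belongs beside item 1.

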6 STATISTICAL CONSIDERATIONS

6.1 Overview

This study is a Phase I, randomized, open-label, dose-escalation study to examine the dose, safety, tolerability, and immunogenicity of VRC-WEVLP073-00-VP (WEVEE) alone or with alum adjuvant at Day 0 and Week 8. The primary objective relates to safety and tolerability; the secondary and exploratory objectives relate to the immunogenicity of the study product.

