6.3 Sample Size and Accrual

Recruitment will target 30 healthy adult participants divided equally among 6 groups.

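### The study sets out to examine dose, but the plan gives no estimate with an interval of how neutralising titre differs between 6, 30 and 60 mcg

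*Combined protocol and SAP*

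**What the plan says.** Section 4 describes a trial "to examine the dose, safety, tolerability, and immune response to the WEVEE vaccine alone or with alum adjuvant at three doses", and section 6.1 repeats the description: a "dose-escalation study to examine the dose, safety, tolerability, and immunogenicity of" the vaccine. Section 6.3 sets the size: "Recruitment will target 30 healthy adult participants divided equally among 6 groups", that is, 5 per group and 10 per dose level. Table 1 allows some more: "Up to 10 subjects over target accrual are permitted to be allocated to any group".

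Two places deal with differences between groups. Section 6.3.3: "For groupwise difference in immunogenicity, a simple comparison on the positive response rate will be used". It introduces Table 4 as the power of Fisher's test for any pair of schedules, and says that the table "indicates that this study is not powered for group comparison". Section 6.4.4 says that Fisher's "exact tests will be used to compare the two vaccine groups to each other"; with six groups, the two are not identified.

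The rest of the immunogenicity analysis is descriptive: response rates with exact 95% intervals, longitudinal graphs, and tables and plots of the continuous readouts, log-transformed if that helps. There is no dose term, no GMT ratio between doses, and no analysis that combines the subjects at one dose level across alum.

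**The concern.** Dose is part of the stated purpose, and neutralising titre 4 weeks after the second vaccination is the main immunogenicity measure. A reader of the report will compare titres across 6, 30 and 60 mcg whether or not an analysis is planned. With summaries alone, that comparison is made by eye between groups of five, with no statement of uncertainty.

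The planned test does not fill the gap. It turns titre into responder or non-responder and compares two groups at a time. The protocol's closest precedent suggests that this may carry no information on dose. Section 1.4.1 reports that, with the predecessor alphavirus VLP vaccine, every subject had neutralising antibody by 4 weeks after the second dose, which is the primary immunogenicity time point here. The same section compares GMTs between that trial's dose groups, so titre by dose is a question the sponsor has already asked of a sister product.

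**Working it through.** **1. The plan's own figure.** Enumerating all outcomes of two Binomial(5, p) groups and rejecting when two-sided Fisher p is at most 0.05 (the plan states no alpha) reproduces all 16 cells of Table 4 within 1 point. For example, 0.1 v 0.5 gives 12.1% (printed 12), 0.2 v 0.6 gives 14.2% (printed 14), and 0.1 v 0.3 gives 1.9% (printed 1).

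**2. What Fisher can show at 5 v 5.** Only 0/5 v 4/5, 0/5 v 5/5 and 1/5 v 5/5, with their mirror images, reach p ≤ 0.05. Near ceiling nothing does: 5/5 v 5/5 and 4/5 v 5/5 both give p = 1.0, and 3/5 v 5/5 gives p = 0.44. If every group responds as in section 1.4.1, no dose difference can appear, however far apart the titres are.

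**3. Precision of a titre estimate.** The documents give no titre SD, so log10 SD (s) of 0.3 to 0.6 is assumed. The 95% CI for the 60/6 mcg GMT ratio is the estimate multiplied and divided by 10^(t × SE). Since 60/6 = 10, this is also the ratio per 10-fold dose.

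- *Two groups of 5.* SE = s√(2/5); 8 df, t = 2.306.
- *Log-dose slope, one formulation, n = 15.* The log10 doses are 0.778, 1.477 and 1.778, with mean 1.344. The sum of squared deviations is 0.526 per subject at each dose, so SE = s/√(5 × 0.526); 13 df, t = 2.160.
- *Log-dose slope plus alum term, n = 30.* Alum is balanced within dose, so SE = s/√(10 × 0.526); 27 df, t = 2.052.
- *Dose as three categories plus alum term, n = 30.* SE = s√(2/10); 26 df, t = 2.056.

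| Analysis | t × SE, s = 0.3 | Factor, s = 0.3 | t × SE, s = 0.6 | Factor, s = 0.6 |
|---|---|---|---|---|
| 5 v 5 | 0.437 | 2.7 | 0.875 | 7.5 |
| Slope, one formulation | 0.399 | 2.5 | 0.799 | 6.3 |
| Slope, pooled over alum | 0.268 | 1.9 | 0.537 | 3.4 |
| Dose categories, pooled over alum | 0.276 | 1.9 | 0.552 | 3.6 |

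**4. Where the gain comes from.** Using the order and spacing of the doses within one formulation narrows the factor only from 2.7–7.5 to 2.5–6.3. Using all 30 subjects narrows it to 1.9–3.4. Treating dose as three categories is almost as precise, so the estimate need not rest on a straight line.

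The same decomposition in power, for an assumed 3-fold rise from 6 to 60 mcg, s from 0.3 to 0.6, and the Fisher cut-off midway between the two means: Fisher 5 v 5, 34% down to 9%; 5 v 5 t-test on titre, 60% to 20%; single-formulation slope, 67% to 22%; pooled slope, 94% to 42%. The large steps are from response rate to titre and from one formulation to both.

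**The case against.** The strongest reply is that nobody promised a dose comparison. The objectives in sections 3.1 and 3.2 evaluate safety and immunogenicity with and without adjuvant, and the hypotheses in section 4 are that the vaccine is safe and elicits responses. None asks how one dose compares with another. In a first-in-human trial the working dose question is safe escalation, which section 4.3 covers. The plan also says plainly that it lacks power for group comparison. All of this stands. It limits the weight of the point, but it does not supply the missing estimate: low power is a reason to report an interval, not to omit one.

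A reader might infer that dose is in fact addressed, by pairwise Fisher tests of 5 v 5. The documents do not settle this. The pairwise reading rests on section 6.3.3. The wording of section 6.4.4 could equally mean alum against no alum, the only contrast that is randomised (section 6.5), and then dose gets no test at all. The titre gap remains under either reading. The optional extra subjects could also make some groups larger than 5.

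A reader might also infer that exploiting the dose order would turn a weak test into a strong one. The contrast of 94–42% with 34–9% changes three things at once: titre for response rate, 30 subjects for 10, and trend for pair. It also depends on an assumed 3-fold rise. At 2-fold the pooled slope has 60% down to 20% power, and section 1.4.1 reports predecessor GMTs that did not differ significantly between dose groups except at week 24. The case therefore rests on estimation, not on power.

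Finally, dose is confounded with enrolment order, because levels open in sequence and randomisation is only within a level. That also stands, and any dose estimate must say so.

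**Conclusion.** The gap is real and of moderate weight. The plan names dose in its purpose, collects titres at three dose levels, and plans no estimate with an interval of how titre differs between them. Its only between-group method works on response rates, does not identify the groups in section 6.4.4, and cannot show a dose difference if nearly everyone responds.

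Under an assumed log10 SD of 0.3 to 0.6, a model on all 30 subjects would place the 60/6 mcg GMT ratio within a factor of about 1.9 to 3.4, against 2.7 to 7.5 for a 5 v 5 titre comparison. That gain assumes the same dose effect with and without alum. Without that assumption, the log-dose slope gives a factor of 2.5 to 6.3.

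The documents do not support calling this a failed objective or a concealed lack of power. Nor do they support a claim that a trend analysis would make the trial adequately powered for dose.

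**What to change.** Add to section 6.4.4, for each of the three viruses at Visit 07: a linear model of log10 neutralising titre on dose and alum, using all subjects. Report GMT ratios between dose levels, or per 10-fold dose, with 95% CIs. Show the dose estimates separately with and without alum beside the pooled ones, as a check on the common dose effect. Label the result descriptive, because dose levels are enrolled in sequence and are not randomised against each other. In the same paragraph, state which groups the Fisher test compares.

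A trend test on response rates is not worth adding, since it would tell little at ceiling.

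The cost is a paragraph of text and one model per virus on data already collected, with no change to doses, visits, sample size or subject risk. There are two statistical costs. If a slope is used, it assumes a log-linear dose effect, which the planned distribution plots can check and which dose categories avoid at little loss. Pooling assumes a common dose effect across alum; if that is wrong, the pooled ratio is an average that describes neither formulation, which is why the separate estimates should be shown.
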